Pre-existing Seizure	NA	Increased frequency from previous level of control without change in seizure character	Change in seizure character either in duration or quality (e.g., severity or focality)	Prolonged and repetitive seizures (e.g., status epilepticus) OR Difficult to control (e.g., refractory epilepsy)
Syncope	Near syncope without loss of consciousness (e.g., pre-syncope)	Loss of consciousness with no intervention indicated	Loss of consciousness AND Hospitalization or intervention required	NA

Pregnancy, Puerperium, and Perinatal

PARAMETER	GRADE 1 MILD	GRADE 2 MODERATE	GRADE 3 SEVERE	GRADE 4 POTENTIALLY LIFE- THREATENING
Fetal Death or Stillbirth (report using mother's participant ID) Report only one	NA	NA	Fetal loss occurring at ≥ 20 weeks gestation	NA
Preterm Delivery ⁷ (report using mother's participant ID)	Delivery at 34 to < 37 weeks gestational age	Delivery at 28 to < 34 weeks gestational age	Delivery at 24 to < 28 weeks gestational age	Delivery at ≤ 24 weeks gestational age
Spontaneous Abortion or Miscarriage ⁸ (report using mother's participant ID) Report only one	Chemical pregnancy	Uncomplicated spontaneous abortion or miscarriage	Complicated spontaneous abortion or miscarriage	NA

⁷ Definition: A delivery of a live-born neonate occurring at ≥ 20 to < 37 weeks gestational age.

⁸ Definition: A clinically recognized pregnancy occurring at < 20 weeks gestational age.

Psychiatric

PARAMETER	GRADE 1 MILD	GRADE 2 MODERATE	GRADE 3 SEVERE	GRADE 4 POTENTIALLY LIFE- THREATENING
Insomnia	Mild difficulty falling asleep, staying asleep, or waking up early	Moderate difficulty falling asleep, staying asleep, or waking up early	Severe difficulty falling asleep, staying asleep, or waking up early	NA
Psychiatric Disorders (includes anxiety, depression, mania, and psychosis) Specify disorder	Symptoms with intervention not indicated OR Behavior causing no or minimal interference with usual social & functional activities	Symptoms with intervention indicated OR Behavior causing greater than minimal interference with usual social & functional activities	Symptoms with hospitalization indicated OR Behavior causing inability to perform usual social & functional activities	Threatens harm to self or others OR Acute psychosis OR Behavior causing inability to perform basic self-care functions
Suicidal Ideation or Attempt Report only one	Preoccupied with thoughts of death AND No wish to kill oneself	Preoccupied with thoughts of death AND Wish to kill oneself with no specific plan or intent	Thoughts of killing oneself with partial or complete plans but no attempt to do so OR Hospitalization indicated	Suicide attempted

Respiratory

PARAMETER	GRADE 1 MILD	GRADE 2 MODERATE	GRADE 3 SEVERE	GRADE 4 POTENTIALLY LIFE- THREATENING
Acute Bronchospasm	Forced expiratory volume in 1 second or peak flow reduced to ≥ 70 to $< 80\%$ OR Mild symptoms with intervention not indicated	Forced expiratory volume in 1 second or peak flow 50 to $< 70\%$ OR Symptoms with intervention indicated OR Symptoms causing greater than minimal interference with usual social & functional activities	Forced expiratory volume in 1 second or peak flow 25 to $< 50\%$ OR Symptoms causing inability to perform usual social & functional activities	Forced expiratory volume in 1 second or peak flow $< 25\%$ OR Life-threatening respiratory or hemodynamic compromise OR Intubation
Dyspnea or Respiratory Distress Report only one	Dyspnea on exertion with no or minimal interference with usual social & functional activities OR Wheezing OR Minimal increase in respiratory rate for age	Dyspnea on exertion causing greater than minimal interference with usual social & functional activities OR Nasal flaring OR Intercostal retractions OR Pulse oximetry 90 to $< 95\%$	Dyspnea at rest causing inability to perform usual social & functional activities OR Pulse oximetry $< 90\%$	Respiratory failure with ventilator support indicated (e.g., CPAP, BPAP, intubation)

Sensory

PARAMETER	GRADE 1 MILD	GRADE 2 MODERATE	GRADE 3 SEVERE	GRADE 4 POTENTIALLY LIFE- THREATENING
Hearing Loss ≥ 12 years of age	NA	Hearing aid or intervention not indicated	Hearing aid or intervention indicated	Profound bilateral hearing loss (> 80 dB at 2 kHz and above) OR Non-serviceable hearing (i.e., >50 dB audiogram and <50% speech discrimination)
< 12 years of age (based on a 1, 2, 3, 4, 6 and 8 kHz audiogram)	> 20 dB hearing loss at ≤ 4 kHz	> 20 dB hearing loss at > 4 kHz	> 20 dB hearing loss at ≥ 3 kHz in one ear with additional speech language related services indicated (where available) OR Hearing loss sufficient to indicate therapeutic intervention, including hearing aids	Audiologic indication for cochlear implant and additional speech-language related services indicated (where available)
Tinnitus	Symptoms causing no or minimal interference with usual social & functional activities with intervention not indicated	Symptoms causing greater than minimal interference with usual social & functional activities with intervention indicated	Symptoms causing inability to perform usual social & functional activities	NA
Uveitis	No symptoms AND Detectable on examination	Anterior uveitis with symptoms OR Medication/laser intervention indicated	Posterior or pan-uveitis OR Operative intervention indicated	Disabling visual loss in affected eye(s)
Vertigo	Vertigo causing no or minimal interference with usual social & functional activities	Vertigo causing greater than minimal interference with usual social & functional activities	Vertigo causing inability to perform usual social & functional activities	Disabling vertigo causing inability to perform basic self-care functions
Visual Changes (assessed from baseline)	Visual changes causing no or minimal interference with usual social & functional activities	Visual changes causing greater than minimal interference with usual social & functional activities	Visual changes causing inability to perform usual social & functional activities	Disabling visual loss in affected eye(s)

Systemic

PARAMETER	GRADE 1 MILD	GRADE 2 MODERATE	GRADE 3 SEVERE	GRADE 4 POTENTIALLY LIFE- THREATENING
Acute Allergic Reaction	Localized urticaria (wheals) with no medical intervention indicated	Localized urticaria with intervention indicated OR Mild angioedema with no intervention indicated	Generalized urticaria OR Angioedema with intervention indicated OR Symptoms of mild bronchospasm	Acute anaphylaxis OR Life-threatening bronchospasm OR Laryngeal edema
Chills	Symptoms causing no or minimal interference with usual social & functional activities	Symptoms causing greater than minimal interference with usual social & functional activities	Symptoms causing inability to perform usual social & functional activities	NA
Cytokine Release Syndrome⁹	Mild signs and symptoms AND Therapy (i.e., antibody infusion) interruption not indicated	Therapy (i.e., antibody infusion) interruption indicated AND Responds promptly to symptomatic treatment OR Prophylactic medications indicated for ≤ 24 hours	Prolonged severe signs and symptoms OR Recurrence of symptoms following initial improvement	Life-threatening consequences (e.g., requiring pressor or ventilator support)
Fatigue or Malaise Report only one	Symptoms causing no or minimal interference with usual social & functional activities	Symptoms causing greater than minimal interference with usual social & functional activities	Symptoms causing inability to perform usual social & functional activities	Incapacitating symptoms of fatigue or malaise causing inability to perform basic self-care functions
Fever (non-axillary temperatures only)	38.0 to < 38.6°C or 100.4 to < 101.5°F	≥ 38.6 to < 39.3°C or ≥ 101.5 to < 102.7°F	≥ 39.3 to < 40.0°C or ≥ 102.7 to < 104.0°F	≥ 40.0°C or ≥ 104.0°F
Pain¹⁰ (not associated with study agent injections and not specified elsewhere) Specify location	Pain causing no or minimal interference with usual social & functional activities	Pain causing greater than minimal interference with usual social & functional activities	Pain causing inability to perform usual social & functional activities	Disabling pain causing inability to perform basic self-care functions OR Hospitalization indicated
Serum Sickness¹¹	Mild signs and symptoms	Moderate signs and symptoms AND Intervention indicated (e.g., antihistamines)	Severe signs and symptoms AND Higher level intervention indicated (e.g., steroids or IV fluids)	Life-threatening consequences (e.g., requiring pressor or ventilator support)

⁹ Definition: A disorder characterized by nausea, headache, tachycardia, hypotension, rash, and/or shortness of breath.

¹⁰ For pain associated with injections or infusions, see the *Site Reactions to Injections and Infusions* section (page 23).

¹¹ Definition: A disorder characterized by fever, arthralgia, myalgia, skin eruptions, lymphadenopathy, marked discomfort, and/or dyspnea.

Systemic

PARAMETER	GRADE 1 MILD	GRADE 2 MODERATE	GRADE 3 SEVERE	GRADE 4 POTENTIALLY LIFE- THREATENING
Underweight ¹² > 5 to 19 years of age	NA	WHO BMI z-score < -2 to ≤ -3	WHO BMI z-score < -3	WHO BMI z-score < -3 with life-threatening consequences
2 to 5 years of age	NA	WHO Weight-for- height z-score < -2 to ≤ -3	WHO Weight-for- height z-score < -3	WHO Weight-for-height z-score < -3 with life- threatening consequences
< 2 years of age	NA	WHO Weight-for- length z-score < -2 to ≤ -3	WHO Weight-for- length z-score < -3	WHO Weight-for-length z-score < -3 with life- threatening consequences
Weight Loss (excludes postpartum weight loss)	NA	5 to < 9% loss in body weight from baseline	≥ 9 to < 20% loss in body weight from baseline	≥ 20% loss in body weight from baseline OR Aggressive intervention indicated (e.g., tube feeding, total parenteral nutrition)

¹² WHO reference tables may be accessed by clicking the desired age range or by accessing the following URLs:
http://www.who.int/growthref/who2007_bmi_for_age/en/ for participants > 5 to 19 years of age and
http://www.who.int/childgrowth/standards/chart_catalogue/en/ for those < 5 years of age.

Site Reactions to Injections and Infusions

Urinary

PARAMETER	GRADE 1 MILD	GRADE 2 MODERATE	GRADE 3 SEVERE	GRADE 4 POTENTIALLY LIFE- THREATENING
Urinary Tract Obstruction	NA	Signs or symptoms of urinary tract obstruction without hydronephrosis or renal dysfunction	Signs or symptoms of urinary tract obstruction with hydronephrosis or renal dysfunction	Obstruction causing life-threatening consequences

..

Laboratory Values Chemistries

PARAMETER	GRADE 1 MILD	GRADE 2 MODERATE	GRADE 3 SEVERE	GRADE 4 POTENTIALLY LIFE- THREATENING
Acidosis	NA	pH \geq 7.3 to < LLN	pH < 7.3 without life-threatening consequences	pH < 7.3 with life-threatening consequences
Albumin, Low (g/dL; g/L)	3.0 to < LLN 30 to < LLN	\geq 2.0 to < 3.0 \geq 20 to < 30	< 2.0 < 20	NA
Alkaline Phosphatase, High	1.25 to < 2.5 x ULN	2.5 to < 5.0 x ULN	5.0 to < 10.0 x ULN	\geq 10.0 x ULN
Alkalosis	NA	pH > ULN to \leq 7.5	pH > 7.5 without life-threatening consequences	pH > 7.5 with life-threatening consequences
ALT or SGPT, High Report only one	1.25 to < 2.5 x ULN	2.5 to < 5.0 x ULN	5.0 to < 10.0 x ULN	\geq 10.0 x ULN
Amylase (Pancreatic) or Amylase (Total), High Report only one	1.1 to < 1.5 x ULN	1.5 to < 3.0 x ULN	3.0 to < 5.0 x ULN	\geq 5.0 x ULN
AST or SGOT, High Report only one	1.25 to < 2.5 x ULN	2.5 to < 5.0 x ULN	5.0 to < 10.0 x ULN	\geq 10.0 x ULN
Bicarbonate, Low (mEq/L; mmol/L)	16.0 to < LLN 16.0 to < LLN	11.0 to < 16.0 11.0 to < 16.0	8.0 to < 11.0 8.0 to < 11.0	< 8.0 < 8.0
Bilirubin Direct Bilirubin¹⁴, High > 28 days of age	NA	NA	> ULN	> ULN with life-threatening consequences (e.g., signs and symptoms of liver failure)
\leq 28 days of age	ULN to \leq 1 mg/dL	> 1 to \leq 1.5 mg/dL	> 1.5 to \leq 2 mg/dL	> 2 mg/dL
Total Bilirubin, High > 28 days of age	1.1 to < 1.6 x ULN	1.6 to < 2.6 x ULN	2.6 to < 5.0 x ULN	\geq 5.0 x ULN
\leq 28 days of age	See Appendix A. Total Bilirubin for Term and Preterm Neonates	See Appendix A. Total Bilirubin for Term and Preterm Neonates	See Appendix A. Total Bilirubin for Term and Preterm Neonates	See Appendix A. Total Bilirubin for Term and Preterm Neonates
Calcium, High (mg/dL; mmol/L) \geq 7 days of age	10.6 to < 11.5 2.65 to < 2.88	11.5 to < 12.5 2.88 to < 3.13	12.5 to < 13.5 3.13 to < 3.38	\geq 13.5 \geq 3.38
< 7 days of age	11.5 to < 12.4 2.88 to < 3.10	12.4 to < 12.9 3.10 to < 3.23	12.9 to < 13.5 3.23 to < 3.38	\geq 13.5 \geq 3.38

¹⁴ Direct bilirubin > 1.5 mg/dL in a participant < 28 days of age should be graded as grade 2, if < 10% of the total bilirubin.

Chemistries

PARAMETER	GRADE 1 MILD	GRADE 2 MODERATE	GRADE 3 SEVERE	GRADE 4 POTENTIALLY LIFE- THREATENING
Calcium (Ionized), High (mg/dL; mmol/L)	> ULN to < 6.0 > ULN to < 1.5	6.0 to < 6.4 1.5 to < 1.6	6.4 to < 7.2 1.6 to < 1.8	≥ 7.2 ≥ 1.8
Calcium, Low (mg/dL; mmol/L) ≥ 7 days of age	7.8 to < 8.4 1.95 to < 2.10	7.0 to < 7.8 1.75 to < 1.95	6.1 to < 7.0 1.53 to < 1.75	< 6.1 < 1.53
< 7 days of age	6.5 to < 7.5 1.63 to < 1.88	6.0 to < 6.5 1.50 to < 1.63	5.50 to < 6.0 1.38 to < 1.50	< 5.50 < 1.38
Calcium (Ionized), Low (mg/dL; mmol/L)	< LLN to 4.0 < LLN to 1.0	3.6 to < 4.0 0.9 to < 1.0	3.2 to < 3.6 0.8 to < 0.9	< 3.2 < 0.8
Cardiac Troponin I, High	NA	NA	NA	Levels consistent with myocardial infarction or unstable angina as defined by the local laboratory
Creatine Kinase, High	3 to < 6 x ULN	6 to < 10 x ULN	10 to < 20 x ULN	≥ 20 x ULN
Creatinine, High	1.1 to 1.3 x ULN	> 1.3 to 1.8 x ULN OR Increase of > 0.3 mg/dL above baseline	> 1.8 to < 3.5 x ULN OR Increase of 1.5 to < 2.0 x above baseline	≥ 3.5 x ULN OR Increase of ≥ 2.0 x above baseline
Creatinine Clearance¹⁵ or eGFR, Low Report only one	NA	< 90 to 60 ml/min or ml/min/1.73 m ² OR 10 to < 30% decrease from baseline	< 60 to 30 ml/min or ml/min/1.73 m ² OR ≥ 30 to < 50% decrease from baseline	< 30 ml/min or ml/min/1.73 m ² OR ≥ 50% decrease from baseline or dialysis needed
Glucose (mg/dL; mmol/L) Fasting, High	110 to 125 6.11 to < 6.95	> 125 to 250 6.95 to < 13.89	> 250 to 500 13.89 to < 27.75	> 500 ≥ 27.75
Nonfasting, High	116 to 160 6.44 to < 8.89	> 160 to 250 8.89 to < 13.89	> 250 to 500 13.89 to < 27.75	> 500 ≥ 27.75
Glucose, Low (mg/dL; mmol/L) ≥ 1 month of age	55 to 64 3.05 to 3.55	40 to < 55 2.22 to < 3.05	30 to < 40 1.67 to < 2.22	< 30 < 1.67
< 1 month of age	50 to 54 2.78 to 3.00	40 to < 50 2.22 to < 2.78	30 to < 40 1.67 to < 2.22	< 30 < 1.67
Lactate, High	ULN to < 2.0 x ULN without acidosis	≥ 2.0 x ULN without acidosis	Increased lactate with pH < 7.3 without life- threatening consequences	Increased lactate with pH < 7.3 with life- threatening consequences

¹⁵ Use the applicable formula (i.e., Cockcroft-Gault in mL/min or Schwartz in mL/min/1.73m²).

Chemistries

PARAMETER	GRADE 1 MILD	GRADE 2 MODERATE	GRADE 3 SEVERE	GRADE 4 POTENTIALLY LIFE- THREATENING
Lipase, High	1.1 to < 1.5 x ULN	1.5 to < 3.0 x ULN	3.0 to < 5.0 x ULN	≥ 5.0 x ULN
Lipid Disorders (mg/dL; mmol/L)				
Cholesterol, Fasting, High ≥ 18 years of age	200 to < 240 5.18 to < 6.19	240 to < 300 6.19 to < 7.77	≥ 300 ≥ 7.77	NA
< 18 years of age	170 to < 200 4.40 to < 5.15	200 to < 300 5.15 to < 7.77	≥ 300 ≥ 7.77	NA
LDL, Fasting, High ≥ 18 years of age	130 to < 160 3.37 to < 4.12	160 to < 190 4.12 to < 4.90	≥ 190 ≥ 4.90	NA
> 2 to < 18 years of age	110 to < 130 2.85 to < 3.34	130 to < 190 3.34 to < 4.90	≥ 190 ≥ 4.90	NA
Triglycerides, Fasting, High	150 to 300 1.71 to 3.42	>300 to 500 >3.42 to 5.7	>500 to < 1,000 >5.7 to 11.4	> 1,000 > 11.4
Magnesium¹⁶, Low (mEq/L; mmol/L)	1.2 to < 1.4 0.60 to < 0.70	0.9 to < 1.2 0.45 to < 0.60	0.6 to < 0.9 0.30 to < 0.45	< 0.6 < 0.30
Phosphate, Low (mg/dL; mmol/L)				
> 14 years of age	2.0 to < LLN 0.81 to < LLN	1.4 to < 2.0 0.65 to < 0.81	1.0 to < 1.4 0.32 to < 0.65	< 1.0 < 0.32
1 to 14 years of age	3.0 to < 3.5 0.97 to < 1.13	2.5 to < 3.0 0.81 to < 0.97	1.5 to < 2.5 0.48 to < 0.81	< 1.5 < 0.48
< 1 year of age	3.5 to < 4.5 1.13 to < 1.45	2.5 to < 3.5 0.81 to < 1.13	1.5 to < 2.5 0.48 to < 0.81	< 1.5 < 0.48
Potassium, High (mEq/L; mmol/L)	5.6 to < 6.0 5.6 to < 6.0	6.0 to < 6.5 6.0 to < 6.5	6.5 to < 7.0 6.5 to < 7.0	≥ 7.0 ≥ 7.0
Potassium, Low (mEq/L; mmol/L)	3.0 to < 3.4 3.0 to < 3.4	2.5 to < 3.0 2.5 to < 3.0	2.0 to < 2.5 2.0 to < 2.5	< 2.0 < 2.0
Sodium, High (mEq/L; mmol/L)	146 to < 150 146 to < 150	150 to < 154 150 to < 154	154 to < 160 154 to < 160	≥ 160 ≥ 160
Sodium, Low (mEq/L; mmol/L)	130 to < 135 130 to < 135	125 to < 130 125 to < 135	121 to < 125 121 to < 125	≤ 120 ≤ 120
Uric Acid, High (mg/dL; mmol/L)	7.5 to < 10.0 0.45 to < 0.59	10.0 to < 12.0 0.59 to < 0.71	12.0 to < 15.0 0.71 to < 0.89	≥ 15.0 ≥ 0.89

¹⁶ To convert a magnesium value from mg/dL to mmol/L, laboratories should multiply by 0.4114.

Hematology

PARAMETER	GRADE 1 MILD	GRADE 2 MODERATE	GRADE 3 SEVERE	GRADE 4 POTENTIALLY LIFE- THREATENING
Absolute CD4+ Count, Low (cell/mm ³ ; cells/L) > 5 years of age (not HIV infected)	300 to < 400 300 to < 400	200 to < 300 200 to < 300	100 to < 200 100 to < 200	< 100 < 100
Absolute Lymphocyte Count, Low (cell/mm ³ ; cells/L) > 5 years of age (not HIV infected)	600 to < 650 0.600 x 10⁹ to < 0.650 x 10⁹	500 to < 600 0.500 x 10⁹ to < 0.600 x 10⁹	350 to < 500 0.350 x 10⁹ to < 0.500 x 10⁹	< 350 < 0.350 x 10⁹
Absolute Neutrophil Count (ANC), Low (cells/mm ³ ; cells/L) ≥ 7 days of age	800 to 1,000 0.800 x 10⁹ to 1.000 x 10⁹	600 to 799 0.600 x 10⁹ to 0.799 x 10⁹	400 to 599 0.400 x 10⁹ to 0.599 x 10⁹	< 400 < 0.400 x 10⁹
2 to 7 days of age	1,250 to 1,500 1.250 x 10⁹ to 1.500 x 10⁹	1,000 to 1,249 1.000 x 10⁹ to 1.249 x 10⁹	750 to 999 0.750 x 10⁹ to 0.999 x 10⁹	< 750 < 0.750 x 10⁹
≤ 1 day of age	4,000 to 5,000 4.000 x 10⁹ to 5.000 x 10⁹	3,000 to 3,999 3.000 x 10⁹ to 3.999 x 10⁹	1,500 to 2,999 1.500 x 10⁹ to 2.999 x 10⁹	< 1,500 < 1.500 x 10⁹
Fibrinogen, Decreased (mg/dL; g/L)	100 to < 200 1.00 to < 2.00 OR 0.75 to < 1.00 x LLN	75 to < 100 0.75 to < 1.00 OR ≥ 0.50 to < 0.75 x LLN	50 to < 75 0.50 to < 0.75 OR 0.25 to < 0.50 x LLN	< 50 < 0.50 OR < 0.25 x LLN OR Associated with gross bleeding
Hemoglobin¹⁷, Low (g/dL; mmol/L) ¹⁸ ≥ 13 years of age (male only)	10.0 to 10.9 6.19 to 6.76	9.0 to < 10.0 5.57 to < 6.19	7.0 to < 9.0 4.34 to < 5.57	< 7.0 < 4.34
≥ 13 years of age (female only)	9.5 to 10.4 5.88 to 6.48	8.5 to < 9.5 5.25 to < 5.88	6.5 to < 8.5 4.03 to < 5.25	< 6.5 < 4.03

¹⁷ Male and female sex are defined as sex at birth.¹⁸ The conversion factor used to convert g/dL to mmol/L is 0.6206 and is the most commonly used conversion factor. For grading hemoglobin results obtained by an analytic method with a conversion factor other than 0.6206, the result must be converted to g/dL using the appropriate conversion factor for the particular laboratory.

Hematology

PARAMETER	GRADE 1 MILD	GRADE 2 MODERATE	GRADE 3 SEVERE	GRADE 4 POTENTIALLY LIFE- THREATENING
57 days of age to < 13 years of age (male and female)	9.5 to 10.4 5.88 to 6.48	8.5 to < 9.5 5.25 to < 5.88	6.5 to < 8.5 4.03 to < 5.25	< 6.5 < 4.03
36 to 56 days of age (male and female)	8.5 to 9.6 5.26 to 5.99	7.0 to < 8.5 4.32 to < 5.26	6.0 to < 7.0 3.72 to < 4.32	< 6.0 < 3.72
22 to 35 days of age (male and female)	9.5 to 11.0 5.88 to 6.86	8.0 to < 9.5 4.94 to < 5.88	6.7 to < 8.0 4.15 to < 4.94	< 6.7 < 4.15
8 to ≤ 21 days of age (male and female)	11.0 to 13.0 6.81 to 8.10	9.0 to < 11.0 5.57 to < 6.81	8.0 to < 9.0 4.96 to < 5.57	< 8.0 < 4.96
≤ 7 days of age (male and female)	13.0 to 14.0 8.05 to 8.72	10.0 to < 13.0 6.19 to < 8.05	9.0 to < 10.0 5.59 to < 6.19	< 9.0 < 5.59
INR, High (not on anticoagulation therapy)	1.1 to < 1.5 x ULN	1.5 to < 2.0 x ULN	2.0 to < 3.0 x ULN	≥ 3.0 x ULN
Methemoglobin (% hemoglobin)	5.0 to < 10.0%	10.0 to < 15.0%	15.0 to < 20.0%	≥ 20.0%
PT, High (not on anticoagulation therapy)	1.1 to < 1.66 x ULN	1.66 to < 2.33 x ULN	2.33 to < 3.00 x ULN	≥ 3.00 x ULN
Platelets, Decreased (cells/mm ³ ; cells/L)	100,000 to < 124,999 100,000 x 10⁹ to < 124,999 x 10⁹	50,000 to < 100,000 50,000 x 10⁹ to < 100,000 x 10⁹	25,000 to < 50,000 25,000 x 10⁹ to < 50,000 x 10⁹	< 25,000 < 25,000 x 10⁹
PT, High (not on anticoagulation therapy)	1.1 to < 1.25 x ULN	1.25 to < 1.50 x ULN	1.50 to < 3.00 x ULN	≥ 3.00 x ULN
WBC, Decreased (cells/mm ³ ; cells/L)				
> 7 days of age	2,000 to 2,499 2,000 x 10⁹ to 2,499 x 10⁹	1,500 to 1,999 1,500 x 10⁹ to 1,999 x 10⁹	1,000 to 1,499 1,000 x 10⁹ to 1,499 x 10⁹	< 1,000 < 1,000 x 10⁹
≤ 7 days of age	5,500 to 6,999 5,500 x 10⁹ to 6,999 x 10⁹	4,000 to 5,499 4,000 x 10⁹ to 5,499 x 10⁹	2,500 to 3,999 2,500 x 10⁹ to 3,999 x 10⁹	< 2,500 < 2,500 x 10⁹

Urinalysis

PARAMETER	GRADE 1 MILD	GRADE 2 MODERATE	GRADE 3 SEVERE	GRADE 4 POTENTIALLY LIFE- THREATENING
Glycosuria (random collection tested by dipstick)	Trace to 1+ or ≤ 250 mg	2+ or > 250 to ≤ 500 mg	> 2+ or > 500 mg	NA
Hematuria (not to be reported based on dipstick findings or on blood believed to be of menstrual origin)	6 to < 10 RBCs per high power field	≥ 10 RBCs per high power field	Gross, with or without clots OR With RBC casts OR Intervention indicated	Life-threatening consequences
Proteinuria (random collection tested by dipstick)	1+	2+	3+ or higher	NA

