If the severity of an AE could fall in either one of two grades (i.e., the severity of an AE could be either grade 2 or grade 3), sites should select the higher of the two grades.

Laboratory Values

General. An asymptomatic, abnormal laboratory finding without an accompanying AE should not be reported to DAIDS in an expedited timeframe unless it meets protocol-specific reporting requirements. Sites should refer to the applicable network standards for reporting abnormal laboratory findings on the CRFs.

Values below Grade 1. Any laboratory value that is between the ULN and grade 1 (for high values) or the LLN and grade 1 (for low values) should not be graded or reported as an AE. Sites should consult the *Manual for Expedited Reporting of Adverse Events to DAIDS, Version 2.0* and their protocol when making an assessment of the need to report an AE.

Overlap of Local Laboratory Normal Values with Grading Table Ranges. When local laboratory normal values fall within grading table laboratory ranges, the severity grading is based on the ranges in the grading table unless there is a protocol-specific grading criterion for the laboratory

Instructions for Use

value. For example, "Magnesium, Low" has a grade 1 range of 1.2 to < 1.4 mEq/L, while a particular laboratory's normal range for magnesium may be 1.3 to 2.8 mEq/L. If a study participant's magnesium laboratory value is 1.3 mEq/L, the laboratory value should be graded as grade 1.

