## **8.2 Clinical laboratory data**

The following clinical laboratory parameters will be measured (see section [12.1](#)):

- At the screening visit,
- On Day 1, Week 1, Week 2, Week 4, Week 6, Week 8 (8 or 12 Week Cohorts), Week 10 (12 Week Cohorts), Week 12 (12 Week Cohorts), safety follow-up visit.

Additional measurements are done on Week 3, Week 5 and Week 7 for alanine aminotransferase (ALT) and aspartate aminotransferase.

**Haematology** parameters will be listed and grouped as follows:

- Red blood cells: haemoglobin (g/L), haemoglobin A1C (mmol/mol) only at screening, hematocrit (fraction of 1), mean corpuscular haemoglobin (MCH) (fmol), mean corpuscular

haemoglobin concentration (MCHC) (mmol/L), mean corpuscular volume (MCV) (fL), mean platelet volume (MPV) (fl), erythrocyte sedimentation rate (mm/h), red distribution width (RDW) (%), reticulocytes (G/L and %) and red blood cell count (RBC) (T/L).

- White blood cells: basophils (G/L and %), eosinophils (G/L and %), lymphocytes (G/L and %), monocytes (G/L and %), neutrophils (G/L and %) and white blood cell count (WBC) (G/L).

- Platelets (G/L).

**Blood chemistry parameters** will be listed and grouped as follows:

- Liver function: alanine aminotransferase (ALT) (IU/L), alkaline phosphatase (IU/L), aspartate aminotransferase (AST) (IU/L), total bilirubin ( $\mu\text{mol/L}$ ) and direct bilirubin ( $\mu\text{mol/L}$ ).

- Renal chemistry: creatinine ( $\mu\text{mol/L}$ ) and blood urea nitrogen (BUN) (mmol/L).

- Electrolytes: calcium (mmol/L), chloride (mmol/L), phosphorus (mmol/L), potassium (mmol/L), sodium (mmol/L) and bicarbonates (mmol/L).

- Metabolism parameters: glucose (mmol/L), cholesterol (mmol/L), triglycerides (mmol/L), lipase (IU/L), uric acid ( $\mu\text{mol/L}$ ) and lactate dehydrogenase (LDH) (IU/L).

- Other parameters: albumin (g/L), creatine kinase (CPK) (IU/L), total protein (g/L), alpha fetoprotein (ug/L) only at screening, Alpha-1 Acid Glycoprotein (g/L) only at screening, Beta natriuretic peptide (BNP) and NT-pro-BNP.

**Coagulation** parameters will be listed and grouped as follows:

- Coagulation parameters: prothrombin time (PT) (s), activated partial thromboplastin time (aPTT) (s) and international normalized ratio (INR).

**Urinalysis** parameters will be listed and grouped as follows:

- Planned urinalysis parameters: dipstick determination of pH, specific gravity, glucose, bilirubin, ketones, leukocytes, nitrite, occult blood, protein and urobilinogen.

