- Direct microscopy: in case of abnormal urinalysis parameters (in listing only).

**Hormonology** parameters will be listed as follows: FSH (IU/L) and estradiol (pmol/L)

In case a laboratory test result is *censored* (no numeric value is available, but only a verbatim term), the following rules are applied:

- $< x$  or  $> x \rightarrow$  a numeric value will be imputed by a value exceeding the cut-off value with one unit.
- $\leq x$  or  $\geq x \rightarrow$  imputation by  $x$ .

Laboratory values will be graded based on the following toxicity grading scale: The Division of AIDS Table for Grading the Severity of Adult and Pediatric AEs (“DAIDS grading table”, version of November 2014), Appendix F - protocol version 8.0 of the 13rd of September 2016.

Lab values will also be graded based on WHO grading scale, but summary tables will be based on DAIDS grading scale only.

For haematology, blood chemistry, and coagulation, raw data and changes from baseline (Day 1) if applicable will be described by measurement time, for each cohort.

For all lab parameters with toxicity grade, a summary table with the number and percentage of subjects with treatment emergent grade 1-4 and 3+4 will be generated for each cohort for the worst post-baseline value. The same table will be provided by measurement time.

For haematology and blood chemistry, graphs of individual subject values (spaghetti plots) will be generated for each cohort for the following parameters: ALT, AST, alkaline phosphatase, total bilirubin, direct bilirubin, blood urea nitrogen, creatinine, CPK, BNP, haemoglobin, platelets and white blood cells.

A listing of all values of a parameter over time for any parameter with treatment emergent Grade 3 or 4 will be generated. A listing of all values of a parameter over time for any parameter with treatment emergent abnormal values will be also generated.

Values will be listed (raw data and change from baseline) and laboratory abnormal values will be flagged with their toxicity grades and clinical significance information.

For urinalysis, raw data will be described by measurement time, for each cohort.

Urinalysis values will be listed including direct microscopy if any.

Hormonology parameters will be listed only.

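### Protocol Appendix F prints two conflicting sets of limits for adult low phosphate and for Grade 2 low sodium, and SAP 8.2 does not say which set governs

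*Protocol*

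**What the plan says.** Protocol Appendix F reproduces the DAIDS grading table of November 2014. Phosphate is headed mg/dL then mmol/L, and sodium mEq/L then mmol/L. Protocol 4.2 admits subjects aged 18–70, so the phosphate row for those over 14 years applies.

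- Phosphate, Grade 1: "2.0 to < LLN 0.81 to < LLN"
- Phosphate, Grade 2: "1.4 to < 2.0 0.65 to < 0.81"
- Phosphate, Grade 3: "1.0 to < 1.4 0.32 to < 0.65"
- Phosphate, Grade 4: below 1.0 mg/dL, or below 0.32 mmol/L
- Phosphate in children of 1 to 14 years, Grade 2: "2.5 to < 3.0 0.81 to < 0.97"
- Sodium, Grade 2: "125 to < 130 125 to < 135". Grade 1 is 130 to <135 in both units.

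Where an adverse event could fall in either of two grades, Appendix F says that "sites should select the higher of the two grades".

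SAP 8.2 groups the tests with their units: "Electrolytes: calcium (mmol/L), chloride (mmol/L), phosphorus (mmol/L"), with sodium in mmol/L later in the same list. It grades laboratory values by Appendix F of protocol version 8.0. It also grades by a WHO scale, but says that "summary tables will be based on DAIDS grading scale only". The outputs are counts of treatment-emergent Grades 1 to 4 and Grades 3+4, by cohort.

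**The concern.** A two-unit table should give the same grade whichever unit is read. In the adult phosphate row, 0.81 mmol/L is paired with 2.0 mg/dL. In the row for children of 1 to 14 years the same 0.81 mmol/L is paired with 2.5 mg/dL. Both cannot be right. For sodium, mEq/L and mmol/L are numerically the same, so two different upper limits for Grade 2 cannot both hold.

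This matters because clinical laboratory results are part of the primary endpoint (Protocol 3.2.1), and Protocol 10.4.2 asks for counts of Grade 3 and 4 abnormalities. There is no comparator arm in which a rate shifted by the choice of limits would show itself. The data are also to be pooled with a Phase 2b study (Protocol 10.8), which needs the same limits in both. A programmer holding mmol/L data can follow the SAP to the letter and still arrive at either of two answers.

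**Working it through.** **Inputs.** The adult and paediatric phosphate limits and the sodium limits are those of Appendix F. The conversion is mmol/L = mg/dL × 10/30.974 = mg/dL × 0.3229. The molar mass of phosphorus is a physical constant and is not in the documents, but the table's own paediatric rows give the same factor: 0.97/3.0 = 0.323 and 1.13/3.5 = 0.323. A least-squares line through the origin over the eight paediatric pairs gives 0.3228.

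**Step 1: reproduce the rows that agree.** Converting the paediatric mg/dL limits:

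- 4.5 → 1.453 (printed 1.45)
- 3.5 → 1.130 (printed 1.13)
- 3.0 → 0.969 (printed 0.97)
- 2.5 → 0.807 (printed 0.81)
- 1.5 → 0.484 (printed 0.48)

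All agree to within 0.005 mmol/L.

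**Step 2: the adult row.**

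| Boundary | mg/dL | × 0.3229 | Printed mmol/L | Printed value back in mg/dL |
|---|---|---|---|---|
| Grade 1/2 | 2.0 | 0.646 | 0.81 | 0.81/0.3229 = 2.51 |
| Grade 2/3 | 1.4 | 0.452 | 0.65 | 0.65/0.3229 = 2.01 |
| Grade 3/4 | 1.0 | 0.323 | 0.32 | 0.32/0.3229 = 0.99 |

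The first two boundaries do not reproduce. The third agrees apart from rounding.

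**Step 3: effect on phosphate grades** (boundaries rounded to two decimals).

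| Phosphate, mmol/L | Grade by mmol/L limits | Grade by mg/dL limits |
|---|---|---|
| 0.65 to <0.81 | 2 | 1 if below LLN, otherwise none |
| 0.45 to <0.65 | 3 | 2 |
| 0.32 to <0.45 | 3 | 3 |
| <0.32 | 4 | 4 |

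**Step 4: sodium.** Sodium is monovalent, so 1 mEq/L = 1 mmol/L, and every other sodium cell prints identical pairs.

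- 130 to <135 mmol/L: Grade 1 only by the mEq/L limits, but both Grade 1 and Grade 2 by the mmol/L limits.
- Below 130 mmol/L: the same grade in both units.

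The Grade 3+4 table can therefore change for phosphate but not for sodium.

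**The case against.** Several points on the other side are sound.

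- **No section says which limits the program will use.** SAP 8.2 fixes the unit in which values are listed, not the column used for grading. A reader might infer that results will be graded one step too severely. That assumes both that the mmol/L column is applied and that the mg/dL and mEq/L limits are the correct ones, and the documents establish neither.
- **The source is not available here.** The SAP cites Appendix F of protocol version 8.0. The protocol at hand carries data to 17 February 2017. Whether version 8.0 or the published table has the same cells cannot be seen.
- **The higher-grade rule does not settle sodium.** A reader might infer from it that no low sodium could ever be Grade 1. The rule is addressed to sites grading adverse events. The SAP's own rules for determining grades say nothing on overlaps, so 130 to <135 mmol/L is undefined, not automatically Grade 2.
- **The consequences are bounded.** The discontinuation criterion in Protocol 4.6.1 that turns on laboratory grade uses Grade 4, where the phosphate limits agree and sodium is unaffected. The muscle-injury stopping rules in Protocol 7.5.1 use creatine kinase. Phosphate is only one item in the work-up there, so reading a shifted Grade 3 count as a drug signal is possible but speculative. Appendix F has laboratory adverse events graded on a separate clinical scale. Raw values are summarised and listed, and nothing is tested.

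What survives is the contradiction itself. That the table is a copied standard does not tell the programmer which of two limits to apply.

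**Conclusion.** The defect is real but narrow. Three limits in Appendix F have mmol/L values that disagree with their paired unit: the adult phosphate Grade 1/2 and Grade 2/3 boundaries, and the upper limit of Grade 2 low sodium. The SAP reports both tests in mmol/L and rests its grade summaries on this table without naming the governing limits.

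If the mmol/L limits are applied, phosphate of 0.45 to <0.65 and of 0.65 to <0.81 mmol/L is graded one step higher than by mg/dL (Grade 2 instead of no grade where a value in the upper band is not below the LLN). Only the lower band moves subjects into the Grade 3+4 table. Sodium of 130 to <135 mmol/L has two possible grades. All other values of either test, and Grade 4 throughout, are unaffected apart from rounding.

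How many subjects this would move cannot be worked out. The documents give no distribution of phosphate or sodium and no laboratory lower limit of normal, and the SAP counts only grades that are worse than reference. The arithmetic rests on the phosphate conversion factor, which the table itself confirms, and on the cells being the same in the version that the SAP cites.

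**What to change.** Before grading is programmed, check the adult phosphate row and the Grade 2 low-sodium cell against the source DAIDS table, and state in SAP 8.2 which limits govern.

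If the first-unit limits (mg/dL and mEq/L) govern, the mmol/L limits to specify are:

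- Phosphate: Grade 1, 0.65 to <LLN; Grade 2, 0.45 to <0.65; Grade 3, 0.32 to <0.45; Grade 4, <0.32.
- Sodium: Grade 2, 125 to <130.

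The SAP should say that these replace the mmol/L values printed in Appendix F. If the printed mmol/L limits are to stand for phosphate, it should say that instead. The sodium overlap needs its own resolution, since the mmol/L column cannot separate Grade 1 from Grade 2. The pooled analysis with the Phase 2b study should use the same limits.

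The cost is one check against the source and one line in the SAP. No new data are needed.
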